6.10.4.2 Statistical Analysis Plan (SAP)

A full SAP will be produced prior to the analysis of any data. Both the TSC and DMC will be given the opportunity to comment on the SAP prior to it being signed-off by the CI and lead statistician.

6.10.4.3 Additional Analyses

Adjusted analyses will be undertaken for the outcomes by adjusting for the baseline value of the respective outcome measure. The primary analysis will be that adjusting for baseline.

Additional adjusted analyses may be undertaken for factors known to be associated with the outcome as decided by the TMG prior to analysis.

A sensitivity analysis will be undertaken based on those with a RBC EPA+DHA enrichment of 2.7-fold.

Further exploratory analyses maybe undertaken, but these will be detailed in the SAP prior to analysis.

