5.1.1 Explanation for choice of comparators

N-3 PUFA will be compared with matched placebo as this is the most robust way to determine the efficacy and adverse effects of n-3 PUFA. All patients involved in the trial will continue to receive usual care (defined in section 6.4.5).

Treatment allocation is double-blind to reduce potential bias in reporting of the primary outcome and patient reported secondary outcomes.

5.2 **Objectives**

The primary research hypothesis is that participants treated with n-3 PUFA will have greater improvement in asthma control as measured by the ACQ-6 test at 24 weeks post-randomisation versus participants treated with placebo.

The secondary research hypotheses are that participants treated with n-3 PUFA will:

- Have better asthma control as measured by the ACQ-7 test.
- Have better asthma related quality of life as measured by the asthma quality of life questionnaire (AQLQ).
- Have better health related quality of life measured by the euro-qol (5L-EQ-5D).
- Have better airway calibre as measured by peak expiratory flow (PEF), forced expiratory volume in 1 second (FEV₁) and forced expiratory flow at 50% of vital capacity (FEF₅₀).
- Have better peak nasal inspiratory flow (PNIF).
- Show n-3 PUFA is well tolerated with an acceptable safety profile.

Mechanistic research hypotheses are that the participants treated with n-3 PUFA will:

- Have reduced type 2 airway inflammation as assessed by FeNO, blood eosinophils and sputum eosinophils (subgroup).
- Have reduced urinary leukotriene E4 (uLTE4) and urinary prostaglandin D2 (PGD₂) concentration.
- Have improved Red Blood Cell (RBC) fatty acid concentration.
- Have increased sputum SPMs (subgroup).

Exploratory research hypotheses are:

- that participants treated with n-3 PUFA will have a reduced frequency of asthma attacks.
- those with higher baseline uLTE4 will have a greater response to n-3 PUFA.
- the greatest benefits will be evident in those with low baseline RBC omega-3 index.
- changes in RBC fatty acid concentration will relate to the clinical and mechanistic responses.

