6.3.1.3 Participant Exclusion Criteria

- 1. Tolerant to aspirin or NSAID with no respiratory or nasal reaction on exposure.
- 2. Significant cardiac disease, respiratory disease or other cause for breathlessness which, according to the principal investigator, contributes to the patient's symptoms of breathlessness or other respiratory symptoms to a greater degree than the patient's asthma.
- 3. Severe or uncontrolled co-morbid disease (other than nasal polyps) which is likely to affect the outcome of the study.
- 4. Having had an upper or lower respiratory tract infection requiring antibiotics within four weeks of randomisation.
- 5. Receiving biologic agents.
- 6. Receiving n-3 fatty acid oral supplements or more than two dietary portions of oily fish per week.
- 7. Current smoker or more than 15 pack-year smoking history.
- 8. Consumption of more than 21 units of alcohol per week as alcohol-induced respiratory symptoms are more common in N-ERD.
- 9. Pregnant or breastfeeding women and those less than 4 weeks postpartum.
- 10. Women of Child Bearing Potential (WOCBP) not using a highly effective form of contraceptive for the duration of participation in the study. A woman is considered of childbearing potential (WOCBP), i.e. fertile, following menarche and until becoming post-menopausal unless permanently sterile. Permanent sterilisation methods include hysterectomy, bilateral salpingectomy and bilateral oophorectomy at least 6 weeks prior to enrolment. Pregnancy tests will be required at trial start and at 12 weeks. Highly effective forms of contraception defined as: Methods of birth control which result in a low failure rate (i.e. less than 1% per year) when used consistently and correctly such, as implants, injectables, combined oral contraceptives, some intrauterine devices (IUDs), sexual abstinence (defined as refraining from heterosexual intercourse during the entire period of risk associated with the study treatments) or vasectomized partner. This will apply to all women under 55 years of age unless they are postmenopausal or sterile. Postmenopausal is defined as no menses for 12 months without an alternative medical cause. A high follicle stimulating hormone (FSH) level in the postmenopausal range may be used to confirm a post-menopausal state in women not using hormonal contraception or hormonal replacement therapy. However in the absence of 12 months of amenorrhea, a single FSH measurement is insufficient.

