6.4.1.2 Treatment Schedule

Participants will be asked to take six grams (as 6 x 1g capsules) once daily or in divided doses, with food.

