6.4.2 Placebo Arm

6.4.2.1 Products

Placebo 6g palm olein IV 56 in a white opaque capsule (manufactured to appear identical to IMP).

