A urine sample will be collected at baseline and after 24 weeks of therapy and analysed by radioimmunoassay. uLTE4 reflects 4-series leukotriene pathway and is a biomarker for N-ERD. It will be corrected for urinary creatinine as this standard practice for this metabolite. PGD2 will also be measured using radioimmunoassay and will used to assess the cyclooxygenase pathway. PGD2 was also reduced significantly in the pilot study(46). See section 6.6.2.2 for details about sample collection, storage and transport.

8) Red blood cell fatty acid concentration (to assess adherence and fatty acid status - biological response relationships).

This will be measured at baseline, 12 weeks and 24 weeks. RBCs will be used as the blood lipid pool to assess habitual PUFA status at baseline and in response to intervention. In contrast to plasma fractions such as plasma cholesterol ester or triglycerides, which are variable and reflect recent intakes (last meal up to two weeks), RBC are a tissue which provide a marker of habitual intake in the few months(47) with less biological variability than plasma PUFA pools. For the RBC an increase of approximately 3.2-fold would be predicted following a 4g Omega-3 ethyl ester 90 dose(48). For the sensitivity analysis a 75% adherence cut-off will be used which equates to an RBC EPA+DHA enrichment of 2.7-fold.

9) The differential cell count and concentration of SPMs in sputum (subgroup of 52 patients at baseline and 24 weeks).

Induced sputum will be collected as previously described(31) after inhalation of increasing concentrations of hypertonic saline if possible. Sputum will be processed as described by Pizzichini et al(32). The sputum plugs will be selected from saliva, processed with dithiothreitol (DTT) and centrifuged. Supernatants will be stored at -80°C for analysis of SPM. Total cell count will be calculated and cell viability determined. Cytospins will be prepared and stained by Wright's stain for differential

cell count. For SPM, sputum samples will be acidified, applied to solid-phase extraction cartridges and the eluted SPM will be analysed by liquid chromatography–tandem mass spectrometry as previously described(34).

10) Blood eosinophils.

These will be measured, at baseline, 12 weeks and 24 weeks, in local clinical laboratories using coulter counters.

11) Full blood count, renal and liver function tests, and coagulation. These will be measured in local laboratories at baseline, 12 weeks and 24 weeks.

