6.10.4.4 Analysis Population

The analysis population are defined as:

- a) intention-to-treat (ITT): all randomised individuals analysed according to randomisation regardless of adherence.
- b) If compliance is less than 85% then a pill count compliance analysis also be carried out defining compliance as taking at least 80% of study medication based on pill counts. This will be detailed in the SAP.

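### The red-cell adherence sensitivity analysis is defined by a 2.7-fold enrichment that placebo participants have essentially no way to reach, so it has either no control arm or a non-randomised one

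*Protocol*

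**What the plan says.** Under Additional Analyses, Protocol section 6.10.4.3 commits to one adherence analysis based on a biomarker: "A sensitivity analysis will be undertaken based on those with a RBC EPA+DHA enrichment of 2.7-fold". It names no arm, comparator or estimator.

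Section 6.10.1 (item 8, red blood cell fatty acids) explains the figure: "For the sensitivity analysis a 75% adherence cut-off will be used which equates to an RBC EPA+DHA enrichment of 2.7-fold". The response behind it is given just before: "For the RBC an increase of approximately 3.2-fold would be predicted following a 4g Omega-3 ethyl ester 90 dose(48". The active-arm schedule in section 6.4.1.2 reads: "Participants will be asked to take six grams (as 6 x 1g capsules) once daily or in divided doses, with food".

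Three other places bear on who can meet the cut-off:

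- Section 6.4.2.1, the control product: "Placebo 6g palm olein IV 56 in a white opaque capsule".
- Section 6.3.1.3, an exclusion criterion: "Receiving n-3 fatty acid oral supplements or more than two dietary portions of oily fish per week".
- Section 5.2, an exploratory hypothesis: "the greatest benefits will be evident in those with low baseline RBC omega-3 index".

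Section 6.10.4.4 defines the intention-to-treat population separately, as everyone randomised. It also describes a pill-count analysis, "defining compliance as taking at least 80% of study medication based on pill counts", to be run only if compliance falls below 85% and to be specified in the SAP.

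**The concern.** The analysis set is defined after randomisation by a biomarker that, by design, only one arm's capsules can raise. In the active arm the cut-off works as an adherence measure. In the placebo arm it says nothing about adherence, because a placebo participant who takes every capsule stays near 1-fold.

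That leaves two ways to run the analysis. Applying the rule to everyone removes the control group. Applying it to the active arm alone compares selected adherers with unselected placebo participants.

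The cut-off is also a ratio with the baseline value as its denominator. For the same absolute rise, a participant with low baseline passes and one with high baseline may fail. The filter therefore selects on a characteristic that the protocol itself names as a likely modifier of benefit.

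The stake is interpretation. The analysis is meant to show whether the result changes among people who achieved adequate exposure. As worded it cannot give a randomised answer. Choosing the comparator after unblinding would make the choice data-driven.

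**Working it through.** **Inputs from the protocol.** Predicted enrichment 3.2-fold at 4 g, and cut-off 2.7-fold at 75% adherence (6.10.1). Scheduled dose 6 g (6.4.1.2). 98 randomised 1:1, 20% withdrawal, ACQ-6 SD 0.67, target difference 0.5 (6.7). Evaluable per arm: 49 x 0.8 = 39.2, taken as 39.

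**Step 1. Reproduce the cut-off.** With a rise that is additive over baseline, fold = 1 + adherence x (F - 1), where F is the fold at full adherence. With F = 3.2: 1 + 0.75 x 2.2 = 2.65, which rounds to 2.7. The alternatives 0.75 x 3.2 = 2.40 and 3.2^0.75 = 2.39 do not reproduce it. The additive model is therefore used below.

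**Step 2. Can placebo participants qualify?** Expected fold is 1.0, so only measurement and biological variation can carry someone to 2.7. For an assumed within-person CV per measurement, s = sqrt(ln(1 + CV^2)) and P = 1 - Phi(ln 2.7 / (s x sqrt 2)).

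| Assumed CV | P(fold at least 2.7) | Expected of 39 |
|---|---|---|
| 10% | <0.0001% | 0.0 |
| 20% | 0.02% | 0.0 |
| 30% | 0.8% | 0.3 |
| 40% | 3.4% | 1.3 |

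**Step 3. Calibration against the schedule.** At 4 g, exactly 2.7-fold corresponds to 1.7/2.2 = 77% adherence. If the rise is linear in dose (an assumption), full adherence at 6 g gives F = 1 + 2.2 x 1.5 = 4.3. Then 75% adherence gives 1 + 0.75 x 3.3 = 3.48-fold, and 2.7-fold corresponds to 1.7/3.3 = 52% adherence.

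**Step 4. Dependence on baseline.** For baseline b relative to the reference, fold = 1 + adherence x (F - 1)/b, so the adherence needed to pass is 1.7 x b/(F - 1).

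| Relative baseline | F = 3.2 (4 g) | F = 4.3 (6 g, extrapolated) |
|---|---|---|
| 0.5 | 39% | 26% |
| 0.75 | 58% | 39% |
| 1.0 | 77% | 52% |
| 1.25 | 97% | 64% |
| 1.5 | 116% (cannot pass) | 77% |
| 2.0 | 155% (cannot pass) | 103% (cannot pass) |

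A fully adherent participant fails above 2.2/1.7 = 1.29 times the reference at F = 3.2, and above 3.3/1.7 = 1.94 times at F = 4.3.

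**Step 5. Filtered active arm against all placebo.** This was simulated with 39 per arm and 4,000 repeats. Assumed values: baseline CV 30%; adherence centred on 85% with SD 15 points, limited to 0 to 100%; 10% error on the fold; ACQ-6 SD 0.67. Negative differences favour active.

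| Assumption | F = 3.2 | F = 4.3 |
|---|---|---|
| Active participants kept | 58% | 90% |
| Geometric mean baseline of those kept, relative to the reference | 0.86 | 0.96 |
| No effect, outcome unrelated to baseline or adherence | 0.00 | 0.00 |
| No effect, outcome correlated 0.3 with baseline status | -0.10 | -0.03 |
| No effect, outcome correlated 0.3 with adherence | -0.06 | -0.02 |
| No effect, both correlations | -0.17 | -0.05 |
| True mean effect -0.50, varying by 0.2 per SD of log baseline as section 5.2 supposes | -0.60 | -0.53 |

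The correlations and their signs are assumed, and opposite signs would reverse the direction of the bias. The documents supply none of them.

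**The case against.** The strongest reply is that section 6.10.4.3 does not say the analysis keeps only enriched participants. The figure is presented as an adherence cut-off, and a cut-off of that kind could define adherers in the active arm for a valid complier analysis. Comparator and estimator are details that a SAP often supplies. This stands in part: the loss of the control arm follows from a literal reading and is not stated outright. It does not rescue the rule. The enrichment cut-off is the only population criterion given, and the section's own reference to the SAP attaches to further exploratory analyses. Neither reading of the rule as a subset keeps the randomised comparison.

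The second reply is that the size of the bias is assumed. This stands fully. With the 6 g extrapolation the filter removes only about 10% of the active arm, and the differences under no effect are at most about 0.05 ACQ points. They are zero if outcome is unrelated to baseline and adherence. A reader might infer that the analysis must be biased towards benefit, or that anyone above about 1.3 times the reference baseline fails. The first is not established. The second uses the 4 g response; on the extrapolated 6 g response the point is about 1.94 times.

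The third reply is that little hangs on this analysis. That also stands. A reader might take it as the protocol's principal check on non-adherence, or as a threat to the primary result. No section gives it that role, and the intention-to-treat analysis of all randomised participants does not use the cut-off.

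A reader might also extend the criticism to the pill-count analysis. The documents do not support that: its 80% threshold can be met in either arm, it is conditional on low compliance, and its detail is expressly left to the SAP.

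**Conclusion.** The rule is faulty as stated, and the fault is more than missing detail. Essentially no placebo participant can enter the set (0.0 to 1.3 of 39 at assumed CVs of 10 to 40%). The analysis therefore has either no control arm or a comparison that randomisation no longer protects. In the second case the bias is of unknown size: from zero to about 0.17 ACQ points under no effect in the scenarios tried, and at most about 0.05 if enrichment at 6 g follows linear extrapolation. Selection towards low baseline follows from any fold-change rule when the rise is roughly additive, the model that reproduces 2.7. Its strength depends on the assumed response.

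Separately, the 4 g calibration in section 6.10.1 and the 6 g schedule in section 6.4.1.2 do not match. Under linear extrapolation the stated 75% would be about 52%. The two sections must be reconciled; nothing here says which figure should change.

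The primary analysis, sample size and error rate are untouched. This is a should-fix.

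**What to change.** In section 6.10.4.3, replace the enriched subset with a complier-average causal effect estimate in all randomised participants:

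- Instrument: randomised arm.
- Exposure: change in red-cell EPA+DHA from baseline. A continuous measure is preferable, since participants below the cut-off are still partly treated.
- Method: two-stage least squares for change in ACQ-6 at 24 weeks.
- Adjustment: baseline ACQ-6, baseline red-cell EPA+DHA, study site and participation in the sputum sub-study.
- Status: labelled supportive, with the exclusion restriction (allocation acts on ACQ-6 only through the exposure) and linearity of response stated as assumptions.

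If 2.7-fold is kept anywhere as a description of adherence, sections 6.10.1 and 6.4.1.2 need to be reconciled so that the dose behind the figure is clear.

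The cost is wording in the protocol and SAP, agreed before unblinding. Red-cell samples are already planned for all participants at baseline, 12 and 24 weeks, so no new data are needed. The statistical price is a wider confidence interval and the two stated assumptions. Participants without a follow-up red-cell value would need to be handled under the missing-data provisions of section 6.10.4.5.

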6.10.4.4 Analysis Population

The analysis population are defined as:

- a) intention-to-treat (ITT): all randomised individuals analysed according to randomisation regardless of adherence.
- b) If compliance is less than 85% then a pill count compliance analysis also be carried out defining compliance as taking at least 80% of study medication based on pill counts. This will be detailed in the SAP.

6.10.4.5 Missing Data

The pattern of missing data will be assessed and if appropriate, multiple imputation will be used to account for missing data under the assumption that the data are missing at random. If the data are not considered missing at random then a sensitivity analysis of the results will be undertaken by considering appropriate scenarios, such as the worst-case scenario or pattern-mixture models.

6.10.5 Analysis of Tissue Samples

A laboratory analysis plan for blood, sputum and urine will be agreed and approved by the CI and TMG prior to analysis. In addition, a laboratory manual for sample handling will be developed and agreed by the CI and circulated to sites prior to activation to recruitment.

6.11 Safety reporting

6.11.1 Safety reporting

Adverse events will be collected at each visit and analysed according to the SAP. Adverse events by treatment group will be reviewed regularly by the DMC as described in their Terms of Reference (ToR).

Definitions of harm of the EU Directive 2001/20/EC Article 2 based on the principles of ICH GCP apply to this trial.

Adverse Event (AE)	Any untoward medical occurrence in a patient or clinical trial participant administered a medicinal product and which does not necessarily have a causal relationship with this product
Adverse Reaction (AR)	Any untoward and unintended response to an investigational medicinal product related to any dose administered/trial treatment.
Unexpected Adverse Reaction	An adverse reaction, the nature or severity of which is not
(UAR)	consistent with the applicable product information (e.g.
	Investigator's Brochure for an unauthorised product or SPC for
	an authorised product or treatment.
Serious Adverse Event (SAE) or	Any AE or AR that at any dose:
Serious Adverse Reaction (SAR)	 results in death is life threatening* requires hospitalisation or prolongs existing hospitalisation** results in persistent or significant disability or incapacity is a congenital anomaly or birth defect or is another important medical condition***

 Table 2: Adverse Event Definitions

* the term life threatening here refers to an event in which the patient is at risk of death at the time of the event; it does not refer to an event that might hypothetically cause death if it was more severe (e.g. a silent myocardial infarction).

** Hospitalisation is defined as an in-patient admission, regardless of length of stay, even if the hospitalisation is a precautionary measure for continued observation. Hospitalisation for preexisting conditions (including elective procedures that have not worsened) do not constitute an SAE.

*** Medical judgement should be exercised in deciding whether an AE or AR is serious in other situations. Important AEs or ARs that may not be immediately life threatening or result in death or hospitalisation, but may seriously jeopardise the participant by requiring intervention to prevent one of the other outcomes listed in the table (e.g. a secondary malignancy, an allergic bronchospasm requiring intensive emergency treatment, seizures or blood dyscrasias that do not require hospitalisation, or development of drug dependency).

Adverse events include:

- An exacerbation of a pre-existing illness.
- An increase in the frequency or intensity of a pre-existing episodic event or condition.
- A condition (regardless of whether PRESENT prior to the start of the trial) that is DETECTED after trial drug administration. (This does not include pre-existing conditions recorded as such at baseline as they are not detected after trial drug administration).
- Continuous persistent disease or a symptom present at baseline that worsens following administration of the trial treatment.

Adverse events do NOT include:

- Medical or surgical procedures: the condition that leads to the procedure is the adverse event.
- Pre-existing disease or a condition present before treatment that does not worsen.
- Hospitalisation where no untoward or unintended response has occurred e.g. elective cosmetic surgery.
- Overdose of medication without signs or symptoms.

AEs will be coded according to the current version of the Common Terminology Criteria for Adverse Events (CTCAE) dictionary.

6.11.2 Investigator responsibilities relating to safety reporting

All non-serious AEs and ARs, whether expected or not, should be recorded in the patient's medical notes and reported on the adverse events form of the eCRF within 7 days of report/becoming aware.

All SARs and SAEs should be notified to NCTU immediately after the investigator becomes aware of the event (in no circumstance should this notification take longer than 24 hours).

6.11.2.1 Seriousness assessment

When an AE or AR occurs, the investigator or delegated sub-investigator responsible for the care of the participant must first assess whether or not the event is serious using the definition given in Table 2. If the event is classified as 'serious' an SAE form must be completed and NCTU notified immediately. Investigators will also assess causality of the event(s) according to Table 3.

6.11.2.2 Severity or grading of Adverse Events

The severity of all AEs and/or ARs (serious and non-serious) in this trial should be graded according to CTCAE grading criteria and be assigned a grade 1-5.

